### 6.3.3.2. Definition of an SAE

A serious adverse event is any untoward medical occurrence that, at any dose:

- a. Results in death
- b. Is life-threatening

NOTE: The term 'life-threatening' in the definition of 'serious' refers to an event in which the subject was at risk of death at the time of the event. It does not refer to an event, which hypothetically might have caused death, if it were more severe.

- c. Requires hospitalisation or prolongation of existing hospitalisation

NOTE: In general, hospitalisation signifies that the subject has been detained (usually involving at least an overnight stay) at the hospital or emergency ward for observation and/or treatment that would not have been appropriate in the physician's office or out-patient setting. Complications that occur during hospitalisation are AEs. If a complication prolongs hospitalisation or fulfills any other serious criteria, the event is serious. When in doubt as to whether "hospitalisation" occurred or was necessary, the AE should be considered serious.

Hospitalisation for elective treatment of a pre-existing condition that did not worsen from baseline is not considered an AE.

- d. Results in disability/incapacity, or

NOTE: The term disability means a substantial disruption of a person's ability to conduct normal life functions. This definition is not intended to include experiences of relatively minor medical significance such as uncomplicated headache, nausea, vomiting, diarrhea, influenza, and accidental trauma (e.g. sprained ankle) which may interfere or prevent everyday life functions but do not constitute a substantial disruption.

- e. Is a congenital anomaly/birth defect
- f. Medical or scientific judgment should be exercised in deciding whether reporting is appropriate in other situations, such as important medical events that may not be immediately life-threatening or result in death or hospitalisation but may jeopardise the subject or may require medical or surgical intervention to prevent one of the other outcomes listed in the above definition. These should also be considered serious. Examples of such events are invasive or malignant cancers, intensive treatment in an emergency room or at home for allergic bronchospasm, blood dyscrasias or convulsions that do not result in hospitalisation, or development of drug dependency or drug abuse.

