#### **6.3.5. Death Events**

In addition, all deaths will require a specific death data collection tool to be completed. The death data collection tool includes questions regarding cardiovascular (including sudden cardiac death) and noncardiovascular death.

This information should be recorded in the specific death eCRF within one week of when the death is first reported.

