#### **8.3.5.1. Efficacy Analyses**

In this study, data will be summarised as mean, medium, standard deviation, maximum, and minimum for continuous variables, and in tables of frequencies and percentages for categorical variables.

The primary outcomes of this study were the 5-year cumulative incidence rates of HCC, calculated by the Kaplan–Meier method.

Univariate and multivariable analysis by Cox proportional hazards regression model was performed to identify factors associated with HCC. Variables may include serum albumin, total bilirubin, and ALT levels, HBeAg status, serum HBV DNA titer and response to treatment, etc. Effect sizes are expressed as hazard ratios (HRs) and 95% confidence intervals (CIs).

The detail of primary, secondary and other efficacy endpoint analysis will be included in the RAP.

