5. STUDY ENDPOINTS

5.1 Primary endpoint

- The cumulative incidence of newly diagnosed hepatocellular carcinoma (HCC) at Week 240, the subject must meet one of the following criteria:
 - Without HCC before Week 24
 - A histological diagnosis of HCC (i.e. by biopsy or at post-mortem);
 - In patients with nodules > 2 cm, identification of typical HCC characteristics (hypervascular in the arterial phase with washout in the portal venous or delayed phases) by 4-phase multidetector CT scan or dynamic contrast-enhanced MRI;
 - In patients with nodules > 1 cm, identification of typical HCC characteristics by both techniques (4-phase multidetector CT and dynamic contrast-enhanced MRI).
- The cumulative incidence of disease progression at Week 240, defined as the first occurrence of any one of the following criteria:
 - An increase in Childs-Pugh score (as defined in Appendix 2) of 2 or more points from baseline;
 - An increase in Childs-Pugh score of 2 or more points, solely based on laboratory parameters (i.e. bilirubin, prothrombin time and/or albumin), confirmed between two consecutive visits at least one month apart;
 - Spontaneous bacterial peritonitis (with proven sepsis);
 - Renal insufficiency defined as a decrease in creatinine clearance to ≤ 50 mL/minute confirmed on two occasions at least one week apart (calculated from serum creatinine concentration);
 - Bleeding gastric/oesophageal varices;
 - Hepatocellular carcinoma;
 - Liver-related death.

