7. STATISTICAL ANALYSIS

7.1 Subject screening, disposition and protocol deviations

The screening failure subjects and the reasons for screening failure will be summarized by the numbers and percentages. The percentages are based on the number of screening failure subjects.

The disposition of subjects will be summarized, including the numbers and percentages of subjects for the following categories: all enrolled subjects, subjects completed the study, subjects early discontinued from the study, subjects in the modified intent to treat population, subjects in the per-protocol population, and subjects in the safety analysis population. All percentages are based on the number of all enrolled subjects.

The primary reason for subject premature discontinuation from study will also be summarized. The reasons for discontinuation will include voluntarily discontinue participation, lost to follow-up, lack of efficacy, subjects with treatment interruptions of ≥ 28 consecutive days, adverse event, intercurrent illness, protocol violations, pregnancy, and other reason. A listing will be provided.

Major protocol deviations will be summarized and listed for mITT population. Subject counts and percentages will be displayed by the following deviation categories:

- Eligibility criteria not met
- Excluded medication, vaccine or device
- Assessment or time point completion
- Wrong study treatment/administration/dose

Major protocol deviations which results in the exclusion of the subject from PP population will be discussed, determined, and documented by study team before final database lock. A listing of subject disposition in analysis data sets will be provide.

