7.4.1 Analysis of primary variables

The primary efficacy endpoints for this study are the 240-Week cumulative incidence of newly diagnosed HCC and 240-Week cumulative incidence of disease progression. The newly diagnosed HCC is defined as HCC cases from Week 24 to Week 240. The analysis will be performed in mITT and PP population.

- Nominal cumulative incidence of newly diagnosed HCC at week 240 is defined as the percentage of patient who are newly diagnosed as HCC from Week 24 visit to Week 240 visit in overall patients. Nominal cumulative incidence of HCC will be summarized by frequency, percentage and its 95% two-sided Wald CI. When the value of the newly diagnosed HCC at week 240 is missing due to the epidemic of COVID-19, the missing value may be imputed with the value at the safety follow-up visit. Different missing imputation scenarios will be assessed for the primary analysis and sensitivity analyses, details are provided in below table in which “Y” means the missing value will be imputed with the value at the safety follow-up visit.

Difference between planned Week 240 visit and actual safety follow up visit	Medication taken after previous visit	Primary Endpoints	Sensitivity Analysis 1	Sensitivity Analysis2
<=28 days	Any	Y	Y	Y
>28 days	GSK	Y	N	Y
	Domestic	Y	N	N
	Both GSK & domestic	Y	N	N
Lost to follow up	NA	N	N	N

- Nominal cumulative incidence of disease progression at week 240 is defined as the percentage of patient who have disease progression before Week 240 visit in overall

patients. Nominal cumulative incidence of disease progression will be summarized by frequency, percentage and its 95% two-sided Wald CI. When the value of the disease progression at week 240 is missing due to the epidemic of COVID-19, the missing value will be imputed with the value at the safety follow-up visit. No sensitive analysis is planned.

- Cumulative incidence of newly diagnosed HCC/disease progression at week 240 and its 95% CI will be estimated from the Kaplan–Meier analysis. Time to newly diagnosed HCC/disease progression is defined as the interval between the date of first treatment dose and the analysis date. The rules of analysis date are described in the following table:

Patient's Condition	Status	Analysis date
Diagnosed HCC/disease progression on visit	Event	Date of diagnosis
Reported SAE related with HCC/disease progression between visits	Event	Date of diagnosis
Complete study without HCC/disease progression	Censor	Date of study complete

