Lost follow up/ Early withdraws	Censor	Date of last visit with the adequate diagnosis data

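### The Kaplan-Meier status table has no rule for death, so deaths without the event are censored as drop-outs: a small upward bias for HCC, and an undefined, untested death component for progression

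*SAP*

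**What the plan says.** Both co-primary endpoints are cumulative incidences at week 240. SAP 7.4.1 says "Cumulative incidence of newly diagnosed HCC/disease progression at week 240 and its 95% CI will be estimated from the" Kaplan-Meier analysis. Protocol 8.3.5.1 agrees for HCC: "The primary outcomes of this study were the 5-year cumulative incidence rates of HCC, calculated by the" Kaplan-Meier method. Neither document names a competing-risk method.

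The SAP 7.4.1 table that sets status and analysis date has four rows:

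- HCC or progression diagnosed at a visit: event, at diagnosis.
- "Reported SAE related with HCC/disease progression between visits": event, at diagnosis.
- Study completed without the event: censored at completion.
- Lost to follow-up or early withdrawal: censored at the "Date of last visit with the adequate diagnosis data".

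SAP 7.4.2.2 applies the same rules at weeks 48 to 192. SAP 7.4.1 also reports a nominal cumulative incidence for each endpoint, which is a crude percentage of all patients with a Wald interval.

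Death appears elsewhere. "Liver-related death" is one component of progression in SAP 5.1. Protocol 6.3.3.2 makes an event serious if it "Results in death". Protocol 6.3.5 requires a data collection tool for every death and says: "The death data collection tool includes questions regarding cardiovascular (including sudden cardiac death) and noncardiovascular death". The discontinuation reasons in SAP 7.1 end with "adverse event, intercurrent illness, protocol violations, pregnancy, and other reason" and do not list death by name.

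**The concern.** A subject who dies without HCC did not have the event and did not complete the study, so only the withdrawal row is left. Kaplan-Meier treats a censored subject as still able to develop HCC later, at the same rate as those who remain. That may be reasonable for a drop-out but is impossible after death. One minus Kaplan-Meier then estimates HCC risk in a hypothetical population in which nobody dies of anything else, and this is never lower than the actual cumulative incidence.

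For progression there is a second difficulty. Whether a death counts as an event or is censored depends on whether it is called liver-related. Neither document defines that term, says who decides, or provides for adjudication. The table also has no date rule for death itself. Without a written rule, these choices would be made at programming, with the deaths in view.

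**Working it through.** **1. The plan's own figure.** Inputs from SAP 3.2.1: p = 0.05, half-width e = 0.034, 95% confidence, 15% drop-out.

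- N = p(1 − p)(z/e)² = 0.0475 × (1.96/0.034)² = 157.8, rounded up to 158.
- Half-width at 158: 1.96 × √(0.0475/158) = 0.0340.
- 158/0.85 = 185.9, rounded up to 186.

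All agree with the plan. The yardstick is therefore 3.4 percentage points.

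**2. HCC: size of the overstatement.** Let c be the true cumulative incidence of HCC at week 240 (5%, the planning value) and d the proportion dying without HCC. The documents give no value for d, so 2%, 5% and 10% are assumed. In 186 subjects that is about 4, 9 and 19 deaths. With constant cause-specific hazards, the cumulative HCC hazard is

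Λ = −ln(1 − c − d) × c/(c + d),

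and one minus Kaplan-Meier tends to 1 − exp(−Λ).

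| d | −ln(0.95 − d) | c/(c + d) | Λ | 1 − KM | Excess over 5% (points) |
|---|---|---|---|---|---|
| 2% | 0.0726 | 0.714 | 0.0518 | 5.05% | 0.05 |
| 5% | 0.1054 | 0.500 | 0.0527 | 5.13% | 0.13 |
| 10% | 0.1625 | 0.333 | 0.0542 | 5.27% | 0.27 |

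The constant-hazard assumption can be dropped for an upper bound. If every such death came before any HCC, the limit would be c/(1 − d), which is 5.10%, 5.26% and 5.56%. The excess is then 0.10, 0.26 and 0.56 points, still well inside 3.4.

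**3. The nominal HCC proportion.** A death without HCC stays in its denominator as a non-event, so this upward bias is absent. It errs the other way under drop-out. With a 5% risk and 15% drop-out at a constant rate, the hazards are −ln(0.95) = 0.0513 and −ln(0.85) = 0.1625. The expected proportion is 0.0513/(0.0513 + 0.1625) × (1 − 0.95 × 0.85) = 0.240 × 0.1925 = 4.6%.

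**4. Progression.** Two effects are separate.

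- *Estimator.* The formula in step 2 applies. The plan gives no expected progression rate. At an assumed 10%, with d from 2% to 10%, the excess is about 0.1 to 0.6 points. Here d covers only deaths that are not called liver-related and have no earlier component.
- *Classification.* Progression is the first occurrence of any component, so a death label matters only if no component came before it. Each such death of disputed cause moves the crude rate by 1/186 = 0.54 points; three would move it by 3/186 = 1.6 points. The number of such deaths is unknown. The nominal proportion does not help, because it uses the same event definition.

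**5. Planned checks.** The two sensitivity analyses for nominal HCC vary only the imputation of week-240 visits missed because of COVID-19. For nominal progression SAP 7.4.1 says none is planned, and it describes none for the Kaplan-Meier estimates.

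**The case against.** Four points count against making more of this.

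**Cause of death.** A reader might infer that it is not collected, or that the form separates only cardiovascular from other deaths. The documents do not support that. Protocol 6.3.5 requires a form for every death, and saying what the form includes is not an exhaustive list. The form itself is not in the documents. The gap is that liver-related is undefined and no adjudication is described. Nor do the documents show that the call is left to the site, since no section assigns it to anyone.

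**Liver deaths.** A reader might infer that they drop out of the progression endpoint. They need not: a fatal event is an SAE, and the second event row can bring it in. That route still needs someone to judge the SAE related to progression. Protocol 6.3.3.1 also keeps expected progression of the studied disease out of adverse event reporting unless it is more severe than expected. The route exists but is not a rule.

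**HCC.** A reader might infer a material bias in the primary result. The figures do not bear this out. Entry is limited to ages 18 to 60 with compensated disease, no hypothesis is tested, and the nominal proportion is reported beside the Kaplan-Meier estimate.

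**Disposition.** SAP 7.1 includes adverse event and other reason, so a death can be recorded there. The missing category is only a further sign that death was not considered.

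These objections limit the size of the problem. They do not supply the missing death rule, define the component or add a check for progression.

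**Conclusion.** The point holds in a limited form. The status table omits death, so by default deaths without the event are censored as drop-outs, and one minus Kaplan-Meier is not the cumulative incidence it is called.

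For HCC the bias is upward and minor: about 0.05 to 0.27 points at 5% incidence, against a 3.4-point margin. This assumes 2% to 10% dying without HCC and constant hazards.

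For progression the issue is modest. A component of a co-primary endpoint has no definition, each disputed death with no earlier component is worth at most 0.54 points on the crude rate, and no planned analysis shows the effect. How many such deaths there will be cannot be told from the documents.

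**What to change.** Before database lock, amend SAP 7.4.1 as follows:

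1. Add a death row for each endpoint, dated at death. Liver-related death is a progression event. Death without HCC, and for progression death not called liver-related in a subject with no earlier component, is a competing event.
2. Estimate both cumulative incidences by Aalen-Johansen, here and at the earlier time points in 7.4.2.2. Keep Kaplan-Meier as a sensitivity analysis, because the protocol names it for HCC, and record the change from the protocol.
3. Add one progression sensitivity analysis that counts death from any cause as an event.
4. State how a death is called liver-related and who makes the call, since items 1 and 2 depend on it.

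The cost is SAP wording and two extra runs on data already required, plus a review of the deaths against the definition. The HCC estimate will be equal or slightly lower. The all-cause progression rate will be equal to or higher than the main one.

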7.4.2 Analysis of secondary variables

7.4.2.1 Nominal Cumulative Incidence and Nominal Incidence by visit

As defined in previous, the nominal cumulative incidence of newly diagnosed HCC and the nominal cumulative incidence of disease progression at Week 48, Week 96, Week 144, and Week 192 will be summarized by frequency, percentage and its 95% two-sided Wald CI. The analysis will be performed in mITT. Figures of nominal cumulative incidence of HCC/disease progress by each visit will be product respectively.

The nominal incidence at visit is defined as the percentage of subjects who had event during the previous visit to the current visit. The nominal incidence of newly diagnosed HCC and disease progression at each visit from Week 36 (Week 36, 48, 60, 72, 84, 96, 108, 120, 132, 144, 156, 168,

180, 192, 204, 216 and 240) will be summarized by frequency, percentage and its 95% two-sided Wald CI.

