### Secondary Endpoints

- Incidence of HCC at Week 48, Week 96, Week 144, and Week 192
- Cumulative incidence of HCC at Week 48, Week 96, Week 144, Week 192 and Week 240
- Cumulative incidence of disease progression at Week 48, Week 96, Week 144 and Week 192, and Week 240
- The mean changes of liver stiffness measurement (LSM) at Week 48, Week 96, Week 144, Week 192 and Week 240
- Proportion of subjects with serum HBV DNA  $< 20$  IU/mL (Roche COBAS Taqman HBV Test) at Week 48, Week 96, Week 144, Week 192 and Week 240.
- The mean  $\log_{10}$  reduction in serum HBV DNA at Week 48, Week 96, Week 144, Week 192 and Week 240 compared with baseline.
- The proportion of subjects with ALT normalization at Week 48, Week 96, Week 144, Week 192 and Week 240 in subjects who have abnormal ALT at baseline.

- For HBeAg positive subjects: the proportion of subjects achieving HBeAg loss, HBeAg seroconversion or HBsAg loss and HBsAg seroconversion at Week 24, Week 48, Week 96, Week 144, Week 192 and Week 240.
- For HBeAg negative subjects: the proportion of subjects achieving HBsAg loss and HBsAg seroconversion at Week 48, Week 96, Week 144, Week 192 and Week 240.
- Incidence of virological breakthrough as defined by  $\geq 1 \log_{10}$  increase in HBV DNA from nadir (as determined by two sequential HBV DNA measurements at least 1 month apart, or the last on-treatment measurement) up to Week 48, Week 96, Week 144, Week 192 and Week 240
- The proportion of subjects with histological improvement (a reduction of two or more points in the Knodell necroinflammatory score with no increase in fibrosis) at Week 216 in the subset of subjects with paired baseline and W216 liver biopsies.
- The proportion of subjects with cirrhosis reversal (a reduction of one or more points in the Ishak score and no evidence of cirrhosis) at Week 216 in the subset of subjects with paired baseline and W216 liver biopsies and with a baseline Ishak score higher than or equal to five.
- Subject safety as determined by adverse events and laboratory assessments.

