7.4.2.2 Cumulative incidence by visit

The cumulative incidence of newly diagnosed HCC and the cumulative incidence of disease progression at week 48, week 96, week 144, and week 192 will be estimated from the Kaplan–Meier analysis. Event or censoring rules are the same with cumulative incidence of week 240, as described in section 7.4.1. Figures of nominal cumulative incidence of HCC/disease progress by each visit will be product respectively.

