9. MOCK TABLES, LISTINGS AND GRAPHS (TLGS)

Mock TLGs will be provided in a separate document.

TFL	Number	Title
Table	1.1	Disposition
Table	1.2	Major Protocol Deviations - mITT
Table	2.1.1	Demographics - mITT
Table	2.1.2	Baseline Characteristics - mITT
Table	3.1	Compliance and Duration of the Study Drug - mITT
Table	4.1.1	The Nominal Cumulative Incidence of Newly Diagnosed Hepatocellular Carcinoma (HCC) at Week 240 - mITT
Table	4.1.2	The Nominal Cumulative Incidence of Newly Diagnosed Hepatocellular Carcinoma (HCC) at Week 240 - PP
Table	4.1.3	The Cumulative Incidence of Newly Diagnosed Hepatocellular Carcinoma (HCC) - mITT
Table	4.1.4	The Cumulative Incidence of Newly Diagnosed Hepatocellular Carcinoma (HCC) - PP
Table	4.2.1	The Nominal Cumulative Incidence of Disease Progression at Week 240 - mITT
Table	4.2.2	The Nominal Cumulative Incidence of Disease Progression at Week 240 - PP
Table	4.2.3	The Cumulative Incidence of Disease Progression - mITT

Table	4.2.4	The Cumulative Incidence of Disease Progression - PP
Table	4.3.1	The Nominal Cumulative Incidence of Newly Diagnosed Hepatocellular Carcinoma (HCC) by Visit - mITT
Table	4.3.3	The Nominal Incidence of Newly Diagnosed Hepatocellular Carcinoma (HCC) by Visit - mITT
Table	4.4.1	The Nominal Cumulative Incidence of Disease Progression by Visit - mITT
Table	4.5.1	The Proportion of Subjects with Virological Response (Serum HBV DNA <20 IU/mL) by Visit - mITT
Table	4.5.1.1	The Proportion of Subjects with Virological Response (Serum HBV DNA <20 IU/mL) by Baseline HBeAg Status (HBeAg Positive and HBeAg Negative) by Visit - mITT
Table	4.5.1.2	The Proportion of Subjects with Virological Response (Serum HBV DNA <20 IU/mL) by Baseline HBV DNA Level (≥ 6 Log ₁₀ IU/mL and <6 Log ₁₀ IU/mL) by Visit - mITT
Table	4.5.3	The Proportion of Subjects with Virological Response (Serum HBV DNA <69 IU/mL) by Visit - mITT
Table	4.6.1	The Proportion of Subjects with ALT Normalization (Lab) at Week 48, 96, 144, 192 and 240 in Subjects Who Have Abnormal ALT at Baseline - mITT
Table	4.6.1.1	The Proportion of Subjects with ALT Normalization (AASLD Criteria) at Week 48, 96, 144, 192 and 240 in Subjects Who Have Abnormal ALT at Baseline - mITT
Table	4.7.1	The Proportion of Subjects Achieving HBeAg Loss, HBeAg Seroconversion, HBsAg Loss and HBsAg Seroconversion at Week 48, 96, 144, 192 and 240 for Subjects with Positive HBeAg at Baseline - mITT

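### SAP 7.4.2.1 puts Wald intervals on 17 by-visit HCC rows that expect about half a case each: at the planned 5%, about 10 rows would be [0%, 0%] and coverage is about 40%

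*SAP*

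**What the plan says.** SAP 7.4.2.1 defines the by-visit quantity thus: "The nominal incidence at visit is defined as the percentage of subjects who had event during the previous visit to the current visit". Each row is therefore one interval between visits and is not cumulative. The section lists 17 visits for newly diagnosed HCC and disease progression, from Week 36 on, ending "180, 192, 204, 216 and 240) will be summarized by frequency, percentage and its 95% two-sided Wald CI". Week 228 is not in the list, although Protocol Table 1 schedules it. The HCC output is Table 4.3.3 in SAP section 9, "The Nominal Incidence of Newly Diagnosed Hepatocellular Carcinoma (HCC) by Visit - mITT".

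The same Wald rule applies to nominal cumulative incidence, at Weeks 48 to 192 in 7.4.2.1 and at Week 240 in 7.4.1: "Nominal cumulative incidence of HCC will be summarized by frequency, percentage and its 95% two-sided Wald CI". SAP 6.1 says how a zero count is displayed but not what interval goes with it. The Protocol lists "Incidence of HCC at Week 48, Week 96, Week 144, and Week 192" as a secondary endpoint, separate from cumulative incidence.

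On the estimator, Protocol 8.3.5.1 says: "The primary outcomes of this study were the 5-year cumulative incidence rates of HCC, calculated by the Kaplan–Meier method". SAP 7.4.1 gives the nominal percentage first and then adds: "Cumulative incidence of newly diagnosed HCC/disease progression at week 240 and its 95% CI will be estimated from the" Kaplan-Meier analysis. It does not say which is primary.

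**The concern.** The Wald interval takes its width from the observed proportion, so with no events the width is zero. A row reading 0% with limits 0% and 0% claims certainty and cannot contain any positive rate. With 1 to 3 events the lower limit is negative, which is only cosmetic once truncated at zero. Empty rows are what one expects when a 5% five-year incidence is cut into 12-week pieces.

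Protocol 8.1 states no hypothesis and the sample size was justified by precision, so interval estimates are how the study conveys uncertainty. Here the error has a direction: nearly all misses fall below the truth, which makes HCC look rarer on treatment than the data can support.

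A second, smaller matter is that SAP 7.4.1 reports two Week 240 estimates without ranking them. Its COVID-19 imputation table, with a column for the primary endpoints, sits under the nominal bullet. For disease progression neither document names the primary estimator. The type of Kaplan-Meier interval is not stated.

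**Working it through.** **The plan's own figure.** SAP 3.2.1 and Protocol 8.2.1: N = p(1−p)(z/e)² with p = 0.05, z = 1.960, e = 0.034 gives 157.85, so 158. The half-width at 158 is 3.40%, giving 1.6% to 8.4%, and 158/0.85 = 185.9, so 186. These reproduce.

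**Inputs.** Incidence at Week 240: 5% (SAP 3.2.1). Counting window: Week 24 to Week 240 (SAP 7.4.1), which is 216 weeks or 18 twelve-week intervals. Denominator: the analysis set (SAP 6.1), here mITT, about 186. Rows: 17. Assumptions: an even spread of events and a fixed denominator.

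**By-visit rows.** p = 0.05/18 = 0.278% per row.

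- Expected cases: 186 × 0.00278 = 0.52.
- P(no case) = (1 − 0.00278)^186 = 0.596.
- Expected empty rows: 17 × 0.596 = 10.1. If the Week 240 row spans 24 weeks because Week 228 is not listed, 16 × 0.596 + 0.355 = 9.9.
- Limits at 0 of 186: Wald [0%, 0%]; Clopper-Pearson [0%, 1.96%].
- Limits at 3 of 186: Wald [−0.2%, 3.4%]; Clopper-Pearson [0.3%, 4.6%].

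Exact coverage sums the binomial probabilities of every count whose interval contains p:

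| True Week 240 incidence | Empty rows of 17 | Wald | Clopper-Pearson |
|---|---|---|---|
| 3% | 12.3–12.5 | 26.7% | 99.6% |
| 5% | 9.9–10.1 | 40.4% | 98.4% |
| 8.4% (upper end of the planned interval) | 6.9–7.1 | 58.1% | 98.8% |

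At 5%, 59.6 percentage points of the Wald misses lie below the truth and 0.02 above. Varying n (158 or 186) and the number of equal intervals (17, 18 or 20) gives 9.8 to 11.5 empty rows and Wald coverage of 33% to 42%.

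**Without the even spread.** X events can fill at most X rows, so at least 17 − X rows are empty. With X ~ Binomial(186, 0.05), the mean of max(0, 17 − X) is 7.7, and P(X ≤ 16) = 98.7% is the probability that at least one row must be empty.

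**Nominal cumulative incidence**, n = 186, p = 0.05 × (week − 24)/216:

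| Week | Expected cases | Wald coverage |
|---|---|---|
| 48 | 1.03 | 64.5% |
| 96 | 3.10 | 81.3% |
| 144 | 5.17 | 88.6% |
| 192 | 7.23 | 92.7% |
| 240 | 9.30 | 95.2% |

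At Week 240 Wald coverage is 91.4% for a true 4.5% and 91.5% for 3%. At n = 158 and 5% it is about 89.4%, with 10.0% of intervals below the truth and 0.6% above.

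**Nominal percentage against Kaplan-Meier.** The nominal percentage keeps dropouts in the denominator as event-free. With constant independent hazards (assumption), a true 5% and 15% dropout, the hazards over the period are −ln 0.95 = 0.0513 and −ln 0.85 = 0.1625. The expected nominal value is 0.0513/(0.0513 + 0.1625) × (1 − 0.95 × 0.85) = 4.6%.

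**The case against.** The arithmetic is not in dispute; the weight is. The 17 rows are descriptive and no decision rests on them. SAP 5.2 lists only cumulative incidence, and the Protocol's separate incidence endpoint names four weeks, so at most four rows correspond to a listed endpoint. The count is printed beside each interval, so a reader would see the zero. Kaplan-Meier is already planned at Weeks 48 to 240. The SAP does not say what an empty row prints, and the table shells are in a separate document. At Week 240 coverage is 95.2% at the planning values. Disease progression has no assumed rate and no by-visit interval table in SAP section 9. In SAP 7.4.1 the unqualified term cumulative incidence goes with the Kaplan-Meier bullet, which suggests that Kaplan-Meier is primary.

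Much of this stands and limits the point's importance. The conclusion about Week 240 is not threatened; [0%, 0%] is the formula's value rather than a known printout; every figure here is for HCC. It does not rescue the by-visit rows, for which Wald is the only interval prescribed. Suppressing it in empty rows would leave them with none. The suggestion in 7.4.1 falls short of a statement, and the placement of the imputation column pulls the other way.

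The planned 3.4% margin is a Wald half-width at 158. Clopper-Pearson at 8 of 158 is 2.2% to 9.7%, a half-width of about 3.8%. At the mITT denominator, 9 of 186 gives 2.2% to 9.0%, or (9.0 − 2.2)/2 = 3.4%.

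**Conclusion.** The concern holds. Followed as written, SAP 7.4.2.1 yields by-visit HCC intervals with about 40% coverage at the planned 5% (27% to 58% for true incidences of 3% to 8.4%), and about 10 of 17 rows at [0%, 0%]. The row count and coverage rest on an even spread of events and a denominator of 186; the floor of 7.7 empty rows on average needs no timing assumption. Early nominal cumulative intervals are also too optimistic, with Kaplan-Meier available beside them, and at Week 240 the effect is mild. No size can be given for disease progression. This is a reporting defect that should be corrected; it does not undermine the design. The unranked estimators in 7.4.1 are a lesser point needing a sentence of clarification.

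**What to change.** - In SAP 7.4.1 and 7.4.2.1, replace Wald by Clopper-Pearson for every nominal HCC and disease-progression proportion. If there are no events, report the exact interval for the nominal proportion.
- In SAP 7.4.1, name the Kaplan-Meier estimate at Week 240 as primary for HCC, as Protocol 8.3.5.1 does, and say the same for disease progression. State the Kaplan-Meier interval type, for example complementary log-log.
- Label the nominal percentage descriptive, because it counts dropouts as event-free.
- SAP 7.4.2.2 concerns Kaplan-Meier estimates but asks for "Figures of nominal cumulative incidence of HCC/disease progress by each visit will be product respectively"; remove the word nominal there.

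The cost is SAP wording and a software option. Upper limits rise slightly: at 9 of 186, Wald 1.8% to 7.9% becomes 2.2% to 9.0%. Exact by-visit intervals are conservative, at about 98% coverage. The 158 evaluable and 186 recruited stay as they are.
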